8.1.3. Repeat and Unscheduled Readings

For vital signs measurements and 12-lead ECG data only, any predose value recorded in addition to the original value or a postdose value recorded within 15 minutes of the original value will be defined as a repeat value; any postdose value recorded more than 15 minutes after the original value will be defined as an unscheduled value. For all other data types (eg, laboratory parameters), any value recorded in addition to the original value will be defined as an unscheduled value.

The original scheduled value will be used in all calculations post dose. In the event of any repeats or unscheduled measurements taken pre-dose the values will be considered when determining the baseline value.

As unscheduled values are not associated with any scheduled timepoint, they will be excluded from all calculations, with the exception of the baseline derivation (see Section 8.1.4).

8.1.4. Definitions of Baseline and Change from Baseline

The baseline will be defined as the last non-missing measurement before administration of study drug on Day 1. If the date/time of the value is incomplete or missing, it will be excluded from the baseline calculation, unless the incomplete date/time indicates the value was recorded prior to the first dose.

Individual changes from baseline will be calculated by subtracting the individual subject's baseline value from the value at the postdose timepoint.

The summary statistics for change from baseline will be derived from individual subjects' values (eg, mean change from baseline will be the mean of the individual changes from baseline for all subjects, rather than difference between the mean value at the postdose timepoint and mean value at baseline).

See Section 8.1.3 for more detail on handling repeat and unscheduled readings in the calculations.

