To assess their eligibility to enter the study, potential subjects will be screened within 28 days (Days -29 to -2) and be admitted to the CRU on Day -1 (Check-in).

Subjects will be confined at the CRU from the time of Check-in (Day -1) until EOT on Day 20 upon completion of all PK and safety assessments or Early Termination (ET) if the subject discontinues. Dosing of digoxin will occur on Days 1 through 16 and dosing of LOXO-305 will occur on Days 8 through 16. A follow-up phone call will occur for all

subjects who received at least 1 dose of study drug (including subjects who are terminated early) 7 days (± 2 days) after EOT or ET. The duration of participation is expected to be approximately 58 days (Screening through follow-up phone call).

Figure 3: Study Schematic

Abbreviations: BID = twice daily; EOT = End of Treatment; ET = Early Termination; ICF = Informed Consent Form; PK = pharmacokinetic; QD = once daily.

In this study, physical examinations, 12-lead ECGs, vital sign measurements, How Do You Feel? (HDYF?) inquiries, clinical chemistry panel, coagulation parameters, hematology panel, urinalysis (UA; Appendix 2), safety monitoring of serum digoxin levels, and recording of concomitant medications will be performed at specified times during the study (for specific timepoints and details on each study variable, refer to Appendix 4).

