8.4. Safety Analysis

All safety assessments, including AEs, SAEs, vital sign measurements, clinical laboratory results, safety monitoring of serum digoxin levels, physical examination results, concomitant medications, and 12-lead ECGs, will be tabulated and summarized where possible, using descriptive methodology by treatment, as needed, by timepoint. Unless otherwise specified, baseline value is defined as the last non-missing measurement before administration of study drug on Day 1. No formal statistical analyses are planned for the safety data. All safety data will be listed by subject.

Concomitant medications will be coded using the World Health Organization (WHO) Drug Dictionary (WHO Drug Global B3, September 2019). Adverse events will be coded using Medical Dictionary for Regulatory Activities (MedDRA) Version 22.1 (or higher). The incidence of AEs will be presented by severity and by relationship to study drug as determined by the Investigator or designee (Appendix 1 for AE reporting). All TEAEs will be summarized by system organ class and preferred term.

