| Prior and Concomitant Medications ^t | X | X | X | X | X | X | X | X | X | X | X | X | X | X | X | X | X | X | X | X | X | X | X |
| Serum Pregnancy Test ^u | X | X | _ | | | | | | | | | | | | | | | | | | X | X | |
| FSH Test ^v | X | | _ | | | | | | | | | | | | | | | | | | | | |

Covance Study: 8456071 Protocol Reference: LOXO-BTK-20021

| | Screening | | Treatment Period | | | | | | | | | | | | Clinic Discharge EOT/ET ^w | Follow-up Phone Call (EOS) | | | | | | |
|----------|---------------------|---|------------------|---|---|---|---|---|---|---|----|----|----|----|--|-------------------------------|----|----|----|----|----|--|
| | (Days -29 to -2) | 1 | 2 | 3 | 4 | 5 | 6 | 7 | 8 | 9 | 10 | 11 | 12 | 13 | 14 | 15 | 16 | 17 | 18 | 19 | 20 | 7 (± 2) Days Post EOT/ET ^x |
| TSH Test | X | | | | | | | | | | | | | | | | | | | | | |

Abbreviations: AE = adverse event; BMI = body mass index; BP = blood pressure; COVID-19 = SARS-CoV-2; CRF = Case Report Form; CRU = Clinical Research Unit; ECG = electrocardiogram; eGFR = estimated glomerular filtration rate; EOS = End of Study; EOT = End of Treatment; ET = Early Termination; FSH = follicle-stimulating hormone; HbA1c = hemoglobin A1c; HDYF? = How Do You Feel?; HIV = human immunodeficiency virus; ICF = Informed Consent Form; PK = pharmacokinetic; SAE = serious adverse event; TSH = thyroid-stimulating hormone; UA = urinalysis.

- a. For details on study procedures, see Section 7.
- b. Interim medical history only.
- c. Height collected at Screening only; BMI calculated based on Screening height.
- d. A complete physical examination will be performed at Check-in (Day -1). An abbreviated physical examination will be performed at Day 20 (EOT) or at ET.
- e. 12-lead ECGs will be obtained at Screening and Check-in (Day -1), Day 1 (predose and 2 hours postdose), once daily on Days 2 to 7 (predose), Day 8 (predose and 2 hours postdose), Days 10, 12, and 15 (predose), Day 16 (predose and 2 hours postdose), Day 18, and Day 20 (96 hours postdose on Day 16 [EOT]) or ET. 12-lead ECGs will be collected after the subject has rested in the supine position for at least 10 minutes. When scheduled at the same time as PK blood draws, 12-lead ECGs will be obtained prior to and as close as possible to having blood drawn. The allowed sampling window for 12-lead ECGs is ± 30 minutes from the nominal timepoint for all postdose 12-lead ECGs and no less than 10 minutes prior to dosing for predose 12-lead ECGs.

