1. On Day 8 through Day 16, oral doses of 200 mg LOXO-305 QD will be coadministered with oral doses of 0.25 mg digoxin QD in the morning at the actual time of the Day 1 morning digoxin dose (± 1 hour). LOXO-305 will be administered first, immediately followed by digoxin. On Days 2, 4 through 6, 9 through 11, 13, and 14, subjects will fast for at least 2 hours predose and 1-hour postdose. On Days 3, 12, and 15 where clinical laboratory evaluations are performed, subjects will fast for at least 8 hours predose and 1-hour postdose. On Days 7, 8 and 16, subjects will be fasted at least 10 hours predose and 2 hours postdose. Water will be restricted for 1 hour prior to and 1 hour after dosing with the exception of water administered for dose administration.

- p. Clinical chemistry panel (fasted for at least 8 hours), coagulation parameters, hematology panel, and UA will be performed at Screening, Check-in (Day -1), Day 3 (48 hours postdose on Day 1), Day 7 (predose), Day 12 (predose), Day 15 (predose), and Day 19 (72 hours postdose on Day 16, if the subject completes the study [EOT]), or on the day of ET. At ET or the day before EOT (Day 19), subjects are not required to be fasted prior to clinical laboratory evaluations.
- q. Serum digoxin level samples for safety monitoring will be collected predose on Days 7 through 15 and at the discretion of the Investigator (or designee).
- r. Testing for COVID-19 will be conducted at a minimum at Screening and Check-in (Day -1). Testing for COVID-19 may also be conducted periodically during the subject's CRU confinement, at the discretion of the Investigator (or designee). Tests will be performed by rapid polymerase chain reaction or equivalent.
- s. Urine drug screen for selected drugs of abuse (including cotinine) and alcohol screen (urine or breath).
- t. Prior and concomitant medication administration will be recorded beginning at informed consent. In addition, all Investigator-approved prescription and over-the-counter medications taken by a subject within 14 days or 5 half-lives (if known), whichever is longer, prior to Day 1 will be recorded on the subject's electronic CRF.
- u. Female subjects only. Performed at Screening, Check-in (Day -1), and Day 19 (72 hours postdose on Day 16), if the subject completes the study (EOT) or on the day of ET.
- v. Post-menopausal female subjects only.

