2.2. Secondary Objective

The secondary objective of the study is to assess the safety and tolerability of single and multiple oral doses of LOXO-305 when coadministered with multiple oral doses of digoxin.

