8.6.3. Vital Signs Parameters

All vital signs parameters and their changes from baseline will be listed, as applicable; any value outside the clinical reference range will be flagged, and whether the out of range value was deemed clinically significant or not clinically significant will be indicated.

Summary tables by treatment and timepoint will be provided for all vital signs parameters and their changes from baseline, as applicable.

8.6.4. 12-lead Electrocardiogram Parameters

All 12-lead ECG parameters and their changes from baseline will be listed; any value outside the clinical reference range will be flagged, and whether the out of range value was deemed clinically significant or not clinically significant will be indicated.

Summary tables by treatment and timepoint will be provided for all 12-lead ECG parameters, along with their changes from baseline.

QT interval corrected for heart rate using Fridericia's formula (QTcF) values that are > 450 msec and increase from baseline > 30 msec will be flagged in the data listing.

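### Laboratory, blood pressure, pulse and ECG changes on LOXO-305 plus digoxin are measured only from a pre-digoxin baseline; a supplementary pre-LOXO-305 baseline should be added

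*SAP*

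**What the plan says.** SAP 8.1.4 gives a single definition: "The baseline will be defined as the last non-missing measurement before administration of study drug on Day 1". Protocol 8.4 gives the same rule but leaves room for another: "Unless otherwise specified, baseline value is defined as the last non-missing measurement before administration of study drug on Day 1". Neither document specifies another.

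The two drugs start a week apart (Protocol 3.1): "Dosing of digoxin will occur on Days 1 through 16 and dosing of LOXO-305 will occur on Days 8 through 16".

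SAP 8.6.2 to 8.6.4 tabulate laboratory, vital sign and ECG values and their changes from baseline. For ECGs: "Summary tables by treatment and timepoint will be provided for all 12-lead ECG parameters, along with their changes from baseline". SAP 8.6.4 also flags, in the listing, QTcF values above 450 msec that have risen by more than 30 msec from that baseline.

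The secondary objective in SAP 2.2 is "to assess the safety and tolerability of single and multiple oral doses of LOXO-305 when coadministered with multiple oral doses of digoxin".

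The schedule in Protocol Appendix 4 already includes observations just before LOXO-305 starts. ECG, blood pressure and pulse are taken on Day 1 and then "once daily on Days 2 to 7 (predose), Day 8 (predose and 2 hours postdose), Days 10, 12, and 15 (predose"), with more on Days 16, 18 and 20. Laboratory tests after Day 3 are on "Day 7 (predose), Day 12 (predose), Day 15 (predose), and Day 19 (72 hours postdose on Day 16").

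**The concern.** The secondary objective concerns LOXO-305 given on top of digoxin. SAP 8.6.1 already treats the first LOXO-305 dose on Day 8 as the boundary between treatments when it assigns adverse events. The change scores have no matching reference point: each one on or after Day 8 goes back to a value taken before any digoxin.

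Two things are at stake. First, a shift in an ECG interval, pulse or laboratory value that arose on digoxin alone is carried into the changes reported for the combination, where it can add to or offset a shift that began with LOXO-305. Protocol 1.6 names a laboratory concern specific to LOXO-305, falls in white cells with multiple doses. The Day 12, 15 and 19 changes that bear on it will be measured from a pre-digoxin value although a Day 7 value exists. Second, whether a subject meets the QTcF increase criterion depends partly on what happened in the first week.

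**Working it through.** The plan states no figure for this point, so there is nothing to reproduce. The check has four parts.

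**1. What the reported change contains.** For one subject, with t any time after the first LOXO-305 dose:

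change(t from Day 1) = change(pre-LOXO-305 from Day 1) + change(t from pre-LOXO-305) = d + L

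Here d is the shift over the digoxin-alone period and L is the shift after LOXO-305 is added. The SAP reports d + L. Doses before LOXO-305: 2 on Day 1 plus 1 on each of Days 2 to 7 = 2 + 6 = 8, over 7 days.

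**2. Which parameters can be re-based (Protocol Appendix 4; SAP 8.6).**

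| Data | Last scheduled value before LOXO-305 | Later scheduled values | Affected and fixable? |
|---|---|---|---|
| ECG, blood pressure, pulse | Day 8 predose | Day 8 (2 h), Days 10, 12, 15, 16, 18, 20 | Yes |
| Laboratory tests | Day 7 predose (none on Day 8) | Days 12, 15, 19 | Yes, from Day 7 |
| Respiratory rate, temperature | Check-in | Day 20 | No Day 7 or 8 value |
| Oxygen saturation | Day 1 predose | Day 20 | No Day 7 or 8 value |
| Adverse events | Not applicable | Split at first LOXO-305 dose | Not affected |
| Serum digoxin | Not applicable | Listed only | Not affected |

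**3. Is the Day 7 or Day 8 value close to steady-state digoxin?** Protocol 1.6 gives a half-life of 1.5 to 2 days. Assume one compartment, instantaneous absorption and the Day 1 evening dose 12 h after the morning dose. Let k = ln 2 / half-life and r = exp(-24k). The steady-state trough is r/(1-r) in units of one dose. At Day 8 predose (168 h) the seven morning doses contribute 1 - r^7 of that trough, and the evening dose adds exp(-156k) divided by it. For Day 7 predose (144 h), use r^6 and exp(-132k).

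- Half-life 36 h: r = 0.630, steady-state trough 1.702. Day 7: 0.9375 + 0.0787/1.702 = 0.984. Day 8: 0.9606 + 0.0496/1.702 = 0.990.
- Half-life 48 h: r = 0.707, steady-state trough 2.414. Day 7: 0.875 + 0.1487/2.414 = 0.937. Day 8: 0.9116 + 0.1051/2.414 = 0.955.

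Predose digoxin is therefore about 94% to 99% of its steady-state trough on these two days. Under these assumptions, Day 7 and Day 8 predose values are near-steady-state digoxin-alone references.

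**4. Illustration for the QTcF increase criterion.** The documents give no value for d. Assume -10, 0 or +10 msec.

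| L (msec) | Change from Day 1 at d = -10 / 0 / +10 | Above 30 from Day 1? | Change from Day 8 predose | Above 30 from Day 8? |
|---|---|---|---|---|
| 35 | 25 / 35 / 45 | no / yes / yes | 35 | yes |
| 25 | 15 / 25 / 35 | no / no / yes | 25 | no |

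The same step after LOXO-305 can meet or miss the increase criterion according to d. The 450 msec part of the flag does not depend on the baseline.

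**The case against.** The strongest case against is that this is a deliberate and valid choice. Protocol and SAP agree, the rule is pre-specified, and a drug-free baseline measures the total change on the combination, which is a proper safety quantity. The treatment label names both drugs, so a digoxin effect shown under it is not misattributed, and the objective does not promise to isolate a LOXO-305 increment in these parameters. That stands: the Day 1 baseline should stay.

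A reader might infer that the planned tables cannot show the LOXO-305 step. The documents do not support that. Tables are by timepoint, and individual values and changes are listed. With the same subjects at both times, the mean change from Day 1 at t minus the mean change from Day 1 at Day 8 predose equals the mean within-subject change from Day 8. Missing from the plan are that change as a reported quantity, its SD, and exactness when subjects differ between timepoints. Subjects may be discontinued (Protocol 7.2.6), missing values are not imputed and early-termination data are generally excluded (SAP 8.1.2). SAP 8.1.4 itself prefers the mean of individual changes to a difference of means.

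A reader might also infer that all safety data are affected; the second part of the working shows otherwise.

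Nor is the pre-LOXO-305 value fully clean. There is no control group, so time and confinement effects continue after Day 8. ECG, blood pressure and pulse on Days 2 to 7 are predose only, so no 2-hour value exists on steady-state digoxin alone. The laboratory reference precedes one further digoxin-alone dose, on Day 7. These limits stand and should be stated beside the new tables.

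Finally, safety analysis is descriptive, the QTcF flag is a listing flag that requires both criteria, and LOXO-305 has a separate placebo- and moxifloxacin-controlled QTc study (Protocol 1.4). This lowers the stakes for QTc. It does not supply the change on top of digoxin for laboratory tests, blood pressure, pulse or other ECG parameters.

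**Conclusion.** The point holds as a gap in what is reported. For laboratory tests, blood pressure, pulse and ECG, every change after the first LOXO-305 dose, and the QTcF increase criterion, is d + L; the SAP plans no summary of L with its SD and no flag on it. The carried-over amount equals the Day 1 to Day 7 or 8 shift on digoxin alone. Its size is unknown from the documents, and the 10 msec used above is an assumption for illustration. The decomposition is exact arithmetic; only the near-steady-state check rests on the half-life and the one-compartment assumptions.

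The documents do not support calling the Day 1 baseline an error or saying that the information is lost. The primary PK analysis is untouched. This is a specific improvement from data already collected.

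**What to change.** Keep the Day 1 baseline. Add to SAP 8.1.4 and 8.6.2 to 8.6.4, for the coadministration treatment, a supplementary descriptive change from the last non-missing value before the first LOXO-305 dose: Day 8 predose for ECG, blood pressure and pulse, and Day 7 predose for laboratory tests. Evaluate the QTcF increase against both baselines and show both in the listing.

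State with these outputs that the supplementary change still includes time and confinement effects, that 2-hour postdose values still include the acute postdose digoxin effect, and that the laboratory reference precedes one further digoxin-alone dose. State also that respiratory rate, temperature and oxygen saturation have no Day 7 or Day 8 value and keep the Day 1 baseline only.

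The cost is SAP wording, one more derived baseline in the analysis datasets, and the matching table and listing shells. No new assessments are needed.

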8.2. Subject Disposition and Population Assignment

Subject disposition and population assignment will be listed.

A summary table by treatment sequence will be provided, based on the safety population.

8.3. Screening Demographics

The screening demographics including age, sex, race, ethnicity, height, body weight, and body mass index will be listed.

A summary table by treatment sequence will be provided, based on the safety population.

8.4. Prior and Concomitant Medication

Prior medication will be defined as medication that ends prior to the first dose. Concomitant medication will be defined as medication that starts during or after the first dose or starts but does not end prior to the first dose.

Prior and concomitant medications will be coded using the World Health Organization Drug Dictionary (WHODrug) Global, Format B3, Version September 2020 (or later if a new version is issued during the study; see the data management plan [DMP] for more details). Prior and concomitant medications will be listed.

8.5. Pharmacokinetic Assessments

8.5.1. Pharmacokinetic Analysis

The following plasma PK parameters will be determined where possible from the plasma concentrations of LOXO-305 and digoxin using noncompartmental methods in validated software program Phoenix WinNonlin (Certara, Version 8.1 or higher):

Parameter	Unitsa	Definition
$\mathrm{AUC}_{0\text{-t}}$	h*ng/mL	area under the concentration-time curve from hour 0 to the last measurable concentration $(t_{last})^b$
$\mathrm{AUC}_{\mathrm{tau}}$	h*ng/mL	area under the concentration-time curve over a dosing interval ^b (tau=24 hours)
C_{max}	ng/mL	maximum observed plasma concentration
t_{max}	Н	time to maximum observed plasma concentration
CL/F	L/h	apparent systemic clearance
$MRT_{last} \\$	Н	mean residence time (based on AUC _{0-t})
AR_{AUC}	NA	accumulation ratio base on AUCtau (LOXO-305 only)

NA Not applicable

For each subject, the following urine PK parameters will be calculated, whenever possible, based on the urine concentrations of digoxin:

Parameter	Unitsa	Definition	
Ae	mg	amount excreted in urine per sampling interval (t1-t2)	
CL_R	L/h	renal clearance	

^a Units are based on concentration units (provided by the bioanalytical lab or preferred units for presentation of PK parameters) and dose units used in the study.

^b Area under the concentration-time curve will be calculated using the linear trapezoidal rule for increasing and decreasing concentrations

%feu	%	percentage of dose excreted in urine per sampling interval (t1-t2),
		where CCI

^a Units are based on concentration units (provided by the bioanalytical lab or preferred units for presentation of PK parameters) and dose units used in the study.

Additional PK parameters may be determined where appropriate, e.g. terminal elimination half-life $(t_{1/2})$ after last dose (Day 16) with sample collections up to 96 hours postdose.

The PK analysis will be carried out where possible using actual blood sampling times postdose. If an actual time is missing, the sample concentration result will be treated as missing unless there is scientific justification to include the result using the nominal time.

The parameters C_{max} and t_{max} will be obtained directly from the concentration-time profiles. If C_{max} occurs at more than 1 timepoint, t_{max} will be assigned to the first occurrence of C_{max} .

8.5.1.1. Criteria for the Calculation of Apparent Terminal Elimination Rate Constant and Half-life

The following will be reported only if $t_{1/2}$ is calculable. The start of the terminal elimination phase for each subject will be defined by the pharmacokinetic software and confirmed by visual inspection and generally will be the first point at which there is no systematic deviation from the log-linear decline in concentrations.

The apparent terminal elimination rate constant (λ_z) and its associated half-life ($t_{1/2}$) will only be calculated when a reliable estimate can be obtained using at least 3 data points, preferably not including C_{max} , and the adjusted coefficient for determination of exponential fit (R^2 -adj) of the regression line is ≥ 0.7 .

The following regression-related diagnostic PK parameters will be determined, when possible:

Parameter	Units	Definition	
λ _z Upper	Н	end of exponential fit	
λ_z Lower	Н	start of exponential fit	
$\lambda_z N$	NA	number of data points included in the log-linear regression	
λ_z Span Ratio	NA	time period over which λ_Z was determined as a ratio of $t_{\mbox{\scriptsize 1/2}}$	
R ² -adj	NA	adjusted coefficient for determination of exponential fit	

NA = Not applicable.

Where possible, the span of time used in the determination of λ_z (ie, the difference between λ_z Upper and λ_z Lower) should be ≥ 2 half-lives. If the λ_z Span Ratio is ≤ 2 , the robustness of the $t_{1/2}$ values will be discussed in the CSR.

